Should a participant have any issues regarding their diagnosis or the study they will be able to access help. At recruitment they will be told that for HIV-related queries they can call the HIV/AIDS helpline numbers that are shown in the app. For study-related queries, they can call the study team on the phone numbers that are listed in the study documentation.

Data management & statistical analysis

Data management

Patient recruitment, demographic, baseline and follow-up survey data will be collected by a trained and GCP certified researcher using a mobile device (tablet) connected to the REDCap database. REDCap is a secure web-based application designed for virtually collecting clinical research data and is used by over 150,000 projects around the world (more information at: <http://project-redcap.org/>). The REDCap Android app, which will be installed on the tablets, allows for off-line data collection if there is no internet connection available.

Laboratory results will be added to the NHLS laboratory database as they are received and pushed to the participant through an application layer that is part of the smartphone app. The REDCap database will be connected to the NHLS laboratory database using an API (application programming interface). All HIV-related NHLS laboratory results will be recorded as part of the study to monitor the total number and frequency of laboratory tests on study participants. All data transmission between electronic databases/servers will be secured and encrypted.

Paper records (completed informed consent) will be in the control of study staff for the day they are collected. At the end of each day they will be returned to a centralised location (e.g.: RHI offices) where they will be scanned and archived in a data storage room. Once archived the paper records will only be accessed under special circumstances (e.g.: a patient withdraws or a confirmation of a patient's acceptance to be in the study is required).

Data analysis will be conducted by research staff with all identifying participant data de-identified.

Analysis plan

The primary outcome, linkage to care around 6 months after initial diagnosis, will be available after the final patient recruited has reached the 8 month mark, allowing immediate assessment of the feasibility and immediate impact of the app on initial linkage to care. Thereafter, retention in care, defined as continuation of HIV care (regular clinic visits with laboratory tests and/or medicine pickup) after the linkage to care visit will be assessed 12 months after linkage to care had been made.

Analysis will be done by the study team using STATA. Intention-to-treat will be the primary approach of the analysis and all missing data points will be considered to be loss-to-follow-up. Analysis of the primary outcome will be based on a chi-squared test comparing the proportion of individuals between the study arms and within study sites. A

logistic regression model, with linkage to care as the dependent variable, will be a secondary analysis of the primary outcome.

For secondary outcomes, chi-squared tests will be used for binary variables, Mann-Whitney-U tests for non-normally distributed variables, and t-tests for continuous variables. Relative risk calculations (at 95% confidence) will be used to compute binary variables. Survival analysis will be conducted to determine linkage outcomes at 6 months. A sensitivity analysis will be conducted using regression analysis to identify and adjust for potential confounders.

For the cost-effectiveness analysis, we will have data on direct costs and understand the resource requirements for the development of the app. We will corroborate our existing estimates of the smartphone data costs of the patient. The study team will collect data on clients' opportunity cost as part of the end of the study participant interview as linkage to care (as opposed to non-linkage to care) actually takes more time. We will use primary data collect through this study to calculate unit costs associated to providing HIV services.

From the opportunity cost data collected from patients we will analyse clients' time spent travelling to and being at health facilities to assess service uptake to measure actual patient opportunity cost. The team will separate costs of implementing the SmartLtC intervention and standard of care into categories (e.g. ART, other medicine, laboratory & other tests, health personnel time, overhead and capital costs, patient transport, and lost patient time) which will come from the WHO CHOICE database. Additionally, we will calculate DALY's saved based on disability and deaths averted due to the intervention with weights based on the 2010 Global Burden of Disease Study.

Regulatory compliance

The following methods will be employed to ensure high quality assurance throughout the study period:

- All study staff are GCP trained and certified throughout the study period.
- The study will not start before it receives ethics permission from the University of Witwatersrand Human Research Ethics Committee (Medical) and approval from the district research committee.
- All data collected for the study will be treated sensitively and stored in a secure location (for paper documents) or a secured, password and encrypted database (for electronic records)

Ethics

As a research institute, all RHI research projects go through both internal and external research review. The external review is done through the University of Witwatersrand's ethics board, the Human Subjects Research Committee (HSRC). The SmartLtC study will not start recruiting patients before the committee has reviewed the study and has provided ethics clearance.

Informed consent forms

Informed consent form can be found at the end of this document in Appendix I.

Expected outcomes

This study is expected to have the following outcomes by the end of the project:

- An analysis of the effect of the app in linkage to care for the study population and in different demographic and socioeconomic subgroups
- An understanding of the acceptability of the laboratory result app
- Incremental cost-effectiveness ratio for SmartLTC compared to SOC from the societal perspective and the DOH perspective
- One or more conference presentations on the study and outcomes
- One or more published academic journal articles describing the study and outcomes
- A study report providing recommendations to policy makers, other study teams, and health practitioners.

Dissemination of results and publication policy

Study results will be presented at national and international HIV/AIDS management and clinician conferences and meetings. Study manuscripts will be submitted to the appropriate journals. Results outcomes will be shared at internal and external research days as well as academic meetings. All these dissemination activities will be planned and carried out in close collaboration with the World Bank team.

Duration

Planning is currently ongoing. Recruitment is expected to start: June 1 2015 with 8 months of follow up minimum. Should additional funding be found, a further 12 months of follow-up will be conducted (ending December 2016).

A brief overview is as follows:

Activity	Year 1												Year 2 (to be fully funded)											
	1	2	3	4	5	6	7	8	9	10	11	12	1	2	3	4	5	6	7	8	9	10	11	12
Project launch	█																							
Ethics application		█	█																					
Hiring		█																						
Training		█	█																					
Educational development		█	█	█																				
Smartphone app development		█	█	█	█																			
Patient recruitment						█	█	█																
Data analysis (6 month outcomes at 8 months)															█									
Participant follow-up																		█	█	█				
Data analysis (12 month outcomes at 14th month)																					█			
Report/article writing												█	█								█	█	█	█

Problems anticipated

Potential risks

The largest potential risk revolves around permission from tiers of government for the project to continue. We hope to perform this in different provinces, but are constrained by the limited funding times, so we will need to assess the quickest way forward after we have submitted for permission.

We have noted that funding is not currently committed for year two, and will mobilise internal and other funding should World Bank not be able to commit resources to completing the last phase. A 12 month extension is essential as the primary outcome extends into the second year. The second year will allow the team to look at the effects of the app on ongoing pre-ART monitoring and on patient information concerning VL testing, VL as an adherence tool, and actual viral suppression.

Since the study is voluntary, there is a chance of bias in patient selection. It is possible that more involved patients will want to participate and thus more likely to be linked to care and retained in care (the healthy participant effect). The randomisation process should mitigate some of these issues ensuring the same number of 'involved patients' are in each arm. As with all voluntary studies, there is a chance that the results might not be completely representative of the general population. This is acknowledged here and will also be acknowledged in any study outcomes that are published.

As the app is not hidden from the facility nurses, there is a chance that they might change the care they provide due to fear of being reported by the participant or the app. To minimise the chance of this, the study team will meet with the HIV nursing team prior to recruitment to explain exactly how the app works including what it can and cannot do.

Finally, there is the challenge of making this app broadly available. If the primary outcome is achieved, that is improved linkage to care, we will engage the government to support the national rollout of this application, potentially at the point of first CD4 test.

Limitations

The study team acknowledges that self-testing and door-to-door testing clients will not be included in this trial. This is relevant as South Africa will soon have a large push on home-based HIV testing. However, further studies could include these client populations.

Project management

The project management team is as follows:

Name & organisation	Area of expertise relevant to study	Designation for study	Assigned tasks	% time
[name], RHI	mHealth project management & health care research	Principal Investigator/project manager	Project management	50%
[name], RHI	mHealth project coordination	Project coordinator	Project coordination	50%
[name], RHI	mHealth project coordination	Research assistant	Research assistance	50%
[name], RHI	Data management	Data manager	Data management	25%
[name], NHLS	National Health Laboratory Service	App development & project support	App development management	20%

[name], RHI	HIV technical expert	Support to project	Review of research design and conduct, as well as technical support on HIV educational materials	10%
[name], NHLS	National Health Laboratory Service	Support to project	Review of research design and conduct	10%

Budget

The total budget for the first year of the study is \$200,992 (approximately R2.3 million as of 8 February, 2015). 62% (\$125,108) of this will be used for staff remuneration while the remainder (\$75,814) will be used for non-human resource study expenses including contracting for app development.

Timeline

Detailed timeline of first year:

- January report submitted: 5 February 2015
- Study protocol complete: 11 February 2015
- Site selection: 13 February 2015
- Project start-up workshop: 19 & 20 February 2015
- World Bank protocol review: 24 February 2015
- Wits ethics submission: 6 March 2015
- February report: 9 March 2015
- Expected ethics approval: late March/early April 2015
- Data management system (RedCAP) setup: Feb-Mar 2015
- REDCap ready: March 30 2015
- Submission to and approval from district research team: April 2015
- March report: 3 April 2015
- App development: Feb-April 2015 (App developer sub-contract to be signed in early March - Specifications can be found in Appendix III)
- App testing: April 2015
- Minimum viable product (app): 1 May 2015
- April report: 8 May 2015
- Study recruitment start: 1 June 2015
- May report: 5 June 2015
- June report: 6 July 2015
- July report: 6 August 2015
- Study recruitment end: 31 August 2015
- August report: 7 September 2015 (8th monthly report summarising 8 months of implementation and a contract deliverable)
- Follow-up: June-December 2015
- Data analysis: Nov-Dec 2015
- Draft study report: 11 December 2015
- Expiration of contract: 31 December 2015
- Final report & STATA database: 29 Jan 2016
- Academic manuscript: 1 April 2016

References

- Cheever LW. (2007) Engaging HIV-infected patients in care: their lives depend on it. *Clinical Infectious Disease*. 44(11):1500-02.
- Faal, M., et al. (2011). Providing immediate CD4 count results at HIV testing improves ART initiation. *J Acquir Immune Defic Syndr* 58(3): e54-59.

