Helen Joseph Hospital is approximately 4 km west of Johannesburg's inner-city in the suburb of Auckland Park. As a tertiary clinical site, the hospital provides a number of clinical services including HIV, ANC, PNC, and specialised care services to patients and has a connection with the University of Witwatersrand's Department of Medicine. The area surrounding Helen Joseph Hospital is comprised of mostly black South African middle-income families living in single unit residential dwellings. Helen Joseph Hospital has a catchment population of around 250,000 and an HIV prevalence of approximately 15-20%.

Linkage-to-care rates for all newly diagnosed HIV-positive individuals in both sites are 50-55%. Women have slightly higher linkage rates, at 60%, while men have slightly lower rates, close to 45%. Exact linkage-to-care figures for young adults, those aged between 18 and 25, in this area are unknown. However, previous research has suggested linkage rates for young adults to be 40-45% (Takuva et al 2015). Due to South African laws that protect exploitation of children and the resulting difficulty in including them in research studies, all participants will be 18 years of age or older.

Intervention

This is a multi-site randomised controlled trial in which newly diagnosed HIV-positive patients, fulfilling all inclusion criteria, will be randomised to either receive the intervention (installation of a password-protected laboratory result and HIV-information app on their smartphone) or the standard of care. All patients will be provided with their unique identifier, to present to the clinic, and asked for permission to access their results on the computer, as a means to assess follow up, to phone them and ask them about their experience of HIV care (at the end of the study) and to verify their clinic attendance throughout the study. Participants will be able to provide feedback about the study to the study team by phone or SMS at any time. In return for their time all study participants will receive a R50 study participation allowance, in the form of a mobile phone credit voucher, at the end of their recruitment visit. Participants will be informed that no additional funds will be provided for subsequent appointments.

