Patients randomised to the intervention arm will be assisted with downloading and installing the app, and setting up their accounts with a username, password and PIN. How to use the app including accessing laboratory data and HIV support information will also be explained. All patients will be recruited at first CD4 count test as the classification into 'wellness' or 'treatment' will not occur until their return to the clinic. As standard of care, both wellness and treatment patients are requested to return after 6 months for a follow-up phlebotomy and CD4 count (for wellness patients) or viral load (for patients on ART) testing. All study

participants will be assumed to be linked to care if they attend for the follow up laboratory tests by the end of the 8th month after joining the study. The study team is aware that some patients will need ART bloods at 3 months, and some will need a follow-up VL due to not being suppressed at 6 months. With this in mind, the app will notify the study participant to go for an appointment 6 and 12 months after recruitment irrespective of their initial CD4 count (both wellness and treatment groups). To provide additional support to study participants in the treatment arm, the app will monitor the first viral load result and notify participants with a viral load of >1000 copies/mm³ to go to the clinic in two months, while notifying participants with a viral load of <1000 copies/mm³ to go to the clinic after six months. This logic will be built into the app and is per current South African HIV Guidelines published 24 December 2014 by the National Department of Health.

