The intervention arm will not receive additional or different individualised or real time care, other than at the installation and use of the app; we want to demonstrate the performance of the app in as 'real-world' an environment as possible. Any appointment reminder message sent to the patient will be automated and based on algorithms developed from national guidelines. Use of the app by patients is expected to add to their understanding of HIV and the role of laboratory tests (specifically CD4 counts and viral loads) and ARV medicine as the treatment ensuring their wellbeing. If visits are missed, or monitoring protocols are not followed, this will be noted when the final data are analysed. The team will also monitor use of the app by patients throughout the study to get an understanding which parts of the app were regularly used and how long patients spent reviewing their results or reading other information within the app.

Inclusion criteria

- Newly diagnosed HIV-positive, clients presenting at selected public health facilities, irrespective of CD4 count
- Access to an Android smartphone with data (estimated to be 40-50% of current Hillbrow Community Health Centre (CHC) population)
- Willing to pay the (small) cost to access their laboratory result
- Age – 18 years and older
- Proof of ID/passport/refugee number (for identification/security, and to confirm the single patient identifier)
- Can read English or Zulu
- Ability and willingness to sign informed consent

Exclusion criteria

- Clients presenting for ANC services, as these women will be enrolled in the national MomConnect program
- Refusal to participate

Note that success of the primary objective is not ART initiation, but linkage to care as defined above i.e. *attending for a CD4 count measurement PLUS one other HIV-related NHLS test within 8 months of HIV diagnosis*. This allows the study team to assess linkage to care of patients who are both eligible and not eligible for ART. Traditionally, non-ART eligible patients have been disproportionately lost to follow up and have therefore been included in

this study.

[figure not shown]

Figure 1: Adapted from Health Resources and Services Administration, HIV/AIDS Bureau. Continuum of engagement in HIV care. Cheever LW. Engaging HIV-infected patients in care: their lives depend on it. Clin Infect Dis 2007;44(11):1500-02. Available from <http://www.cdc.gov/hiv/prevention/programs/pwp/linkage.html>

Methodology

Pre-recruitment

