Use of Smartphone App	
 - Patient registration will occur at clinic site with study staff member; Demographic information, photo ID and lab ID required. - Patient will receive an Android notification through their app on their phone when new CD4/VL result is in NHLS database - Patient can view CD4 results (new and historical) on app 
 - NB: CD4 and VL results are colour-coded (red, yellow, green) based on 
 - CD4 level: yellow >500, red < 501 - VL: green below 1001, red above 1000 - Patient can select individual results which will open up an information box explaining what that result means along with a visual-analogue scale showing green to yellow to red and where the patient's CD4 count or viral load sits on the scale - Patient offered FAQ and information sections to learn more about HIV ('basics'. 'signs and symptoms of co-infection, 'sex and hiv'), laboratory results, online resources, and contact information (National AIDS helpline) - Contact numbers (study coordinator, SA AIDS helpline) and 3rd party HIV-related websites provided in app help - Patient to receive further Android notification at 5.5 months and 6 months after app installation to remind about upcoming visit to clinic for additional blood test.
Authorization & Authentication	
At first use:
 
 - Patient to create username (e-mail address?) and password connected to SA ID/Passport number/Refugee number & Lab Requisition ID 
Notes:
 
 - Must create or connect to NHLS database for results! - Server-side user creation 
At subsequent use:
 
 - PIN required at every use of app (similar to Standard Bank android app) 
 - Server-side PIN authentication - PIN and/or password change possible (how?)

App & data security	
Network
 
 - All passwords and patient data encrypted 
App
 
 - All app data to be encrypted - PIN not stored locally
Main screens	
 - Login: UN/PW - PIN code - Lab results - More information - FAQ - Help me (available from any screen)

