3.2 Secondary objective/s

- 3.2.1. To compare ART initiation rates between intervention and control arms.
- 3.2.2. To assess the feasibility and acceptability of receiving laboratory results to a personal smartphone.
- 3.2.3. To assess secondary effects from improved patient information, including return rates after falling out of care (assessed through routine patient record reviews), patient satisfaction (through face-to-face surveys at the 6-month follow-up visit and end of the study), and rates of additional blood tests (especially CD4 count, viral load).
- 3.2.4. To assess patient knowledge levels of their laboratory results.
- 3.2.5. To specifically look at 2 subgroups – men and young adults (18 to 25 years of age), who would particularly benefit from improved linkage to care.
- 3.2.6. To assess the performance of the app in clients with different levels of education and standard of living, and see if there are differences in clinical and usage outcomes
- 3.2.7. To evaluate differences in linkage-to-care, HIV-knowledge, adherence to medication (treatment patients only) and reported quality of life between wellness and treatment patients.
- 3.2.8. To assess the financial and economic costs of providing the SmartLtC smartphone app.
- 3.2.9. To determine the incremental cost, and cost-effectiveness of ART initiation link to the smartphone app (receiving laboratory results and linkage-to-care) as compared to the standard ART initiation.

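### Linkage is to be compared between wellness and treatment patients, but that label is assigned only on return to the clinic, and neither document says how patients who never return are grouped

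*Protocol*

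**What the plan says.** SAP 3.2.7 sets this secondary objective, in the same words as protocol secondary objective 7: "To evaluate differences in linkage-to-care, HIV-knowledge, adherence to medication (treatment patients only) and reported quality of life between wellness and treatment patients".

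The protocol (Study design, Intervention) recruits everyone at the first CD4 test because classification as wellness or treatment "will not occur until their return to the clinic". The same section counts participants as "linked to care if they attend for the follow up laboratory tests by the end of the 8th month after joining the study".

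No other text supplies a label for a patient who does not come back:

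- SAP 6.4 lists age as the only derived variable and time between blood tests as the only computed one.
- SAP 7.4 has no row for wellness and treatment patients.
- The missing-data rules (protocol, Analysis plan; SAP 6.7) deal with missing data points, withdrawals and outliers, not with a missing group label.

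Data that could supply one are collected. CD4 blood is drawn before recruitment (protocol, Recruitment), every HIV-related NHLS result is recorded (Data management), and WHO stage is a field in the recruitment survey (Appendix II).

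**The concern.** The objective treats wellness or treatment as a patient characteristic. As the plan describes it, the label is the product of a clinic visit that takes place after randomisation and that not everyone makes. Making that visit is closely tied to linkage, so whether the label is missing is related to the outcome being compared.

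The protocol also gives a reason to expect the missingness to differ between the groups. Its note after the exclusion criteria says that "non-ART eligible patients have been disproportionately lost to follow up", and these are broadly the wellness patients. The trial includes them for that reason, yet they are the patients most likely to end up without a label. The way they are handled could decide what this objective reports about them.

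**Working it through.** The documents give no rate, sample size or power for this comparison, so there is no figure to reproduce. The check asks what each handling of unlabelled patients does to the result.

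**Inputs from the documents.** Overall linkage is 50–55% (protocol, Study design, Population). Expected recruitment is about 350 (SAP section 5). Patients not eligible for ART are lost more often, with no rate given.

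**Assumed inputs.** All return and linkage rates by group, an equal mix of the two groups, and no linkage among patients who never return.

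**Formulae.** In each group let r = P(return and be labelled) and c = P(linked, given return).

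- True linkage = r × c.
- Linkage among labelled patients only = true linkage / r = c.

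**Illustration.** Treatment: true linkage 60%, r = 80%. Wellness: true linkage 45%, r = 55%.

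- Overall linkage = 0.5 × 60% + 0.5 × 45% = 52.5%, inside the documents' range.
- Unlabelled = 0.5 × 20% + 0.5 × 45% = 32.5%, or about 114 of 350.
- All participants grouped correctly: 60% − 45% = +15 points.
- Unlabelled left out: 0.60/0.80 = 75% v 0.45/0.55 = 82%, about −7 points.
- Unlabelled counted as wellness: treatment stays at 75%; wellness = (0.5 × 0.45)/(0.5 × 0.55 + 0.325) = 0.225/0.600 = 37.5%. The difference is +37.5 points.

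**Sensitivity.** Treatment is held at r = 0.80, c = 0.75 (true linkage 60%), and unlabelled patients are left out:

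| Wellness r | Wellness c | True difference | Labelled-only difference |
|---|---|---|---|
| 0.65 | 0.70 | +14.5 | +5 |
| 0.60 | 0.75 | +15 | 0 |
| 0.55 | 0.80 | +16 | −5 |
| 0.50 | 0.90 | +15 | −15 |

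**Equal return.** With r = 0.70 and c = 0.75 in both groups, true linkage is 52.5% in both and labelled-only linkage is 75% in both, so a null difference stays null. A real difference would be scaled by 1/r; for example 15/0.70 = 21.4 points.

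**Grid.** r and c ran from 0.40 to 1.00 in steps of 0.05, with a wellness share of 0.3, 0.5 or 0.7. Scenarios were kept if overall linkage was 50–55%, the true treatment advantage was at least 5 points, and wellness return was no higher than treatment return. Of 3,690 scenarios, 878 (24%) reverse and 2,157 (58%) shrink without reversing. The other 655 do neither. These are shares of a grid of assumptions, not probabilities.

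**The case against.** The sentence on classification explains why patients are recruited at the first CD4 test; it is not an analysis rule. Other text leans towards keeping everyone. The analysis is by intention to treat, the Intervention section mentions the two groups alongside initial CD4 count, and the note after the exclusion criteria says the endpoint was chosen so that linkage could be assessed whether or not patients are eligible for ART. The data for a baseline grouping appear to be available.

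Much of this stands, and it rules out several stronger readings:

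- **That the plan drops non-returners.** A reader might infer this, but no text says so. No text says they will be kept and labelled either.
- **That an unlabelled patient is by definition not linked.** Return for classification and the follow-up test are separate events. The protocol's background says NHLS can link results across facilities, so a patient who does not return to the study site could still have a second test recorded.
- **That app effects within each group are biased.** Objective 7 compares the two patient groups and does not plan a comparison of arms within them.
- **That the app already supplies the rule.** The line "CD4 level: yellow >500, red < 501" in Appendix III sets a display colour and is not stated to be the classification criterion.

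The objection does not remove the gap. The only label the plan describes depends on return, and two plausible ways of handling its absence pull the result in opposite directions.

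**Conclusion.** The concern holds for one secondary, non-randomised comparison. With the clinic-assigned label, group membership depends on a post-randomisation event closely tied to linkage, and the treatment of unlabelled patients is left open. In the illustration the same data give −7 or +37.5 points against a true +15, according to that choice.

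Those figures rest wholly on assumed rates. A reader might take reversal as the expected result, but the documents give no linkage or return rates by group and do not support that; attenuation is more common in the grid. The direction and size of any bias are unknown. The primary comparison of randomised arms does not use this label and is unaffected.

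**What to change.** In the SAP, add a derived variable that assigns every randomised participant to a wellness or treatment analysis group, whether or not the participant returns. Base it on the recruitment CD4 result in NHLS and, if the team's criterion uses it, the WHO stage recorded at recruitment. The study team should state its criterion before the analysis. Keep all randomised participants in the denominator for linkage, and report how many cannot be classified, by arm.

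The cost is SAP wording and one derived variable, with no new data collection. The drawback is that the baseline-derived group may differ from the clinic's actual classification for some patients. The number is not known, but where both labels exist the agreement can be tabulated.
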